2 PROTOCOL SYNOPSIS

Title A Phase 2, Randomized, Double-blind, Controlled Study to Evaluate the Safety and Efficacy of VX-440 Combination Therapy in Subjects Aged 12 Years and Older With Cystic Fibrosis

Brief Title A Study Evaluating the Safety and Efficacy of VX-440 Combination Therapy in Subjects With Cystic Fibrosis

Clinical Phase and Clinical Study Type Phase 2 safety and efficacy

Objectives **Primary Objectives**

- To evaluate the safety and tolerability of VX-440 in [REDACTED] triple combination with tezacaftor (TEZ) and ivacaftor (IVA)
- To evaluate the efficacy of VX-440 in [REDACTED] triple combination with TEZ and IVA

Secondary Objectives

- To evaluate the pharmacodynamic (PD) effect of VX-440 in [REDACTED] triple combination with TEZ and IVA on sweat chloride concentrations
- To evaluate the pharmacokinetics (PK) of VX-440 when administered in [REDACTED] triple combination with TEZ and IVA
- To evaluate the PK of TEZ, IVA, and their respective metabolites when administered with VX-440

Endpoints **Primary Endpoints**

- Safety and tolerability assessments based on adverse events (AEs), clinical laboratory values, standard 12-lead electrocardiograms (ECGs), vital signs, and pulse oximetry
- Absolute change in percent predicted forced expiratory volume in 1 second (ppFEV₁) from baseline through Day 29 (Parts 1 and 2) [REDACTED]

Secondary Endpoints

- Absolute change in sweat chloride concentrations from baseline through Day 29 (Parts 1 and 2) [REDACTED]
- Relative change in ppFEV₁ from baseline through Day 29 (Parts 1 and 2) [REDACTED]

[REDACTED]

- Absolute change in Cystic Fibrosis Questionnaire-Revised (CFQ-R) respiratory domain score from baseline at Day 29 (Parts 1 and 2) [REDACTED]
- PK parameters of VX-440, TEZ, M1-TEZ, IVA, and M1-IVA

[REDACTED]

Number of Subjects Approximately 198 subjects will be randomized: approximately 42 subjects in Part 1, approximately 24 subjects in Part 2 [REDACTED]

Study Population Male and female subjects with cystic fibrosis (CF)
Part 1: *F508del*/minimal function (MF) genotype, 18 years of age or older
Part 2: *F508del*/*F508del* genotype, 18 years of age or older
[REDACTED]
[REDACTED]

Investigational Drug **Active substance:** VX-440
Activity: CF transmembrane conductance regulatory (CFTR) corrector (increased chloride ion [Cl⁻] secretion)
Strength and route of administration: 200-mg tablet for oral administration

Active substance: TEZ (tezacaftor; VX-661) and IVA (ivacaftor; VX-770)
Activity: CFTR corrector and potentiator (increased Cl⁻ secretion)
Strength and route of administration: 100-mg TEZ/150-mg IVA fixed-dose combination (light yellow) film-coated tablet for oral administration

Active substance: TEZ
Activity: CFTR corrector (increased Cl⁻ secretion)
Strength and route of administration: 50-mg (white) tablet for oral administration

Active substance: IVA
Activity: CFTR potentiator (increased Cl⁻ secretion)
Strength and route of administration: 150-mg IVA (light blue) film-coated tablet for oral administration

Active substance: not applicable
Activity: VX-440-matching placebo, TEZ/IVA-matching placebo, TEZ-matching placebo, IVA-matching placebo
Strength and route of administration: 0-mg film-coated matching placebo tablets for oral administration

Study Duration Part 1

The total study duration is approximately 12 weeks (4 weeks for the Screening Period, 4 weeks for the Treatment Period, and 4 weeks for the Safety Follow-up Period). Subjects will receive study drug for approximately 4 weeks.

Part 2

The total study duration is approximately 20 weeks (4 weeks for the Screening Period, 4 weeks for the Run-in Period, 4 weeks for the Treatment Period, 4 weeks for the Washout Period, and 4 weeks for the Safety Follow-up Period). Subjects will receive study drug for approximately 12 weeks (4 weeks of TEZ/IVA during the Run-in Period, 4 weeks of VX-440 or placebo + TEZ/IVA during the Treatment Period, and 4 weeks of TEZ/IVA during the Washout Period).

[REDACTED]

Study Design

This is a Phase 2, randomized, double-blind, placebo- and TEZ/IVA-controlled, parallel group, multicenter study. The treatment arms and doses of VX-440, TEZ, and IVA to be evaluated are shown in the table below.

Part 1 will consist of 2 cohorts: Cohort 1A and Cohort 1B. The start of dosing of Cohort 1A and Cohort 1B will be sequential. After all Cohort 1A subjects complete the Day 15 Visit, a blinded review of all available safety and PK data will be conducted by the Vertex study team and lead investigator(s). Dosing of Cohort 1B will begin after the blinded review, if supported by safety and PK data.

Part 2 will initiate after the Cohort 1A blinded review, if supported by safety and PK data.

[REDACTED]

Treatment Arms and Planned Doses by Part

[figure not shown]
Part	Treatment Arm	VX-440 Dosage	TEZ Dosage	IVA Dosage
Part 1 Cohort 1A	TC-1A	200 mg q12h	100 mg qd	150 mg q12h
	Triple placebo	Placebo	Placebo	Placebo
Part 1 Cohort 1B	TC-1B-high	600 mg q12h	50 mg q12h	300 mg q12h
	TC-1B-low	200 mg q12h	50 mg q12h	150 mg q12h
	Triple placebo	Placebo	Placebo	Placebo
Part 2	TC-2	600 mg q12h	50 mg q12h	300 mg q12h
	TEZ/IVA	Placebo	100 mg qd	150 mg q12h

[REDACTED]

[figure not shown]
IVA: ivacaftor; q12h: every 12 hours; qd: daily; TBD: to be determined; TEZ: tezacaftor
 Notes: In the “TC-1B-high” and “TC-2” treatment arms, the dosage of VX-440 will be determined based on safety and PK data from Cohort 1A. The planned dose is shown, but may be reduced to 400 mg q12h [REDACTED]

Schematics of the study design are shown below.

[figure not shown]
[figure not shown]
Part 1 Cohort 1A: *F508del/MF* (N ~ 10)
Randomization: 4:1

Part 1 Cohort 1B: *F508del/MF* (N ~ 32)
Randomization: 2:1:1
Stratification: ppFEV₁: ≥70 versus <70

Part 2: *F508del/F508del* (N ~ 24)
Randomization: 3:1
Stratification: ppFEV₁: ≥70 versus <70

Assessments **Safety:** AEs, clinical laboratory assessments, ECGs, vital signs, pulse oximetry, physical examinations (PEs), and ophthalmologic examinations

Efficacy: spirometry, height, weight, CFQ-R [redacted]

PD: sweat chloride

PK: VX-440, TEZ, M1-TEZ, IVA, M1-IVA

Statistical Analyses Primary Objectives:

The primary objectives of the study are the evaluation of safety and tolerability, and efficacy of VX-440 in TC with TEZ/IVA (all parts) [REDACTED]

The safety endpoints include AEs, clinical laboratory values, 12-lead ECGs, vital signs, and pulse oximetry through the Safety Follow-up Visit (all parts). The safety analysis for all treatment groups in all parts will be descriptive only.

The primary efficacy endpoint is the absolute change from baseline through Day 29 for ppFEV₁ (Parts 1 and 2), [REDACTED]. All ppFEV₁ hypothesis tests will be performed within the mixed-effects model for repeated measures (MMRM) framework at a 5% alpha level, with appropriate adjustment for covariates including stratification factors at randomization. The null within-group hypothesis of no difference in the mean absolute change from baseline through the last on-treatment visit (Day 29 or Week 12) for ppFEV₁, in all treatment groups, by part, will be tested using a 2-sided 1-sample *t* test. The adjusted means and 2-sided 95% confidence intervals of the average treatment effects through Day 29 [REDACTED], as applicable, for all within-group and between-group comparisons will be estimated within MMRM.

Secondary Objectives:

A secondary objective of the study is the evaluation of the PD effect of VX-440 in TC with TEZ/IVA (all parts) [REDACTED]

The PD endpoint is the absolute change in sweat chloride from baseline through Day 29 (Parts 1 and 2) [REDACTED]

In Part 1, the null hypothesis of the lack of a decreasing dose-response trend in the mean absolute change from baseline through Day 29 for sweat chloride, between the TC dose groups and placebo will be tested using a multiple comparisons procedure based on the 1-sided maximum *t*-statistic. In all parts, the null within-group hypothesis of no difference in the mean absolute change from baseline through Day 29 [REDACTED], for sweat chloride in all treatment groups, by Part, will be tested using a 2-sided 1-sample *t*-test. The adjusted means and 2-sided 95% confidence intervals of the average treatment effects through Day 29 [REDACTED], for all within-group and between-group comparisons will be estimated within MMRM.

Interim Analyses Separate interim analyses will be performed after:

- all subjects in Part 1 have completed the Safety Follow-up Visit
- all subjects in Part 2 have completed the Safety Follow-up Visit

IDMC Reviews The independent monitoring committee (IDMC) will conduct regular planned safety reviews of study data from all parts of the study as outlined in the IDMC Charter.

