12.3.3.1 Analysis of Primary Efficacy Variables

The primary efficacy variable is the absolute change from baseline for ppFEV₁ through Day 29 in Parts 1 and 2, [REDACTED]. The analysis will be performed using a mixed-effects model for repeated measures (MMRM) with change from baseline as the dependent variable. [REDACTED]

[REDACTED] stratification factors at randomization as categorical covariates, when applicable. The model will be estimated using restricted maximum likelihood. Denominator degrees of freedom for the F test for fixed effects will be estimated using the Kenward-Roger approximation. A compound symmetry covariance structure will be used to model the within-subject errors. Conditional on fixed effects, missing data due to treatment or study discontinuation will be assumed to be missing at random.

Descriptive analyses of the change from baseline will be performed for all treatment groups in Parts 1, 2, [REDACTED]. Adjusted means and 95% confidence intervals of the average treatment effects through Day 29 or Week 12, as applicable, with 2-sided *P* values, will be estimated within MMRM using LSMeans via PROC MIXED in SAS, for all within-group and between-group comparisons in all parts.

[REDACTED]

Further, relevant data from Parts 1, 2, [REDACTED] will be pooled as appropriate within MMRM with appropriate adjustment for covariates. Details will be provided in the SAP.

[REDACTED]

There will be no multiplicity adjustment for performing multiple hypothesis tests.

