### **8.3.1.1 Primary Analysis of the Primary Efficacy Variable**

#### **8.3.1.1.1 Parts 1 and 2**

The null hypothesis to be tested is that the mean absolute within-group change from baseline in percent predicted FEV1 (ppFEV1) through Day 29 is zero for VX-440 in triple combination (TC) with TEZ/IVA, for each part, separately. A 2-sided *p*-value of 0.05 or less will be interpreted as sufficient evidence to reject the null hypothesis.

[figure not shown]
The primary analysis will be performed using a mixed-effects model for repeated measures (MMRM) with change from baseline in ppFEV1 as the dependent variable for each part, separately. This MMRM analysis will include all treatment groups within a part. For Part 1, the analysis will include 3 treatment groups: placebo, pooled TC-1A and TC-1B-low, and TC-1B-high. For Part 2, the analysis will include 2 treatment groups: placebo + TEZ/IVA, and TC-2 (VX-440 + TEZ/IVA). The model will include treatment group, visit, and treatment-by-visit interaction as fixed effects, with the continuous baseline ppFEV1 as a covariate, and will include all data from each treatment group and visit in the analysis. The model will be estimated using restricted maximum likelihood. Denominator degrees of freedom for the F test for fixed effects will be estimated using the Kenward-Roger approximation. An unstructured covariance structure will be used to model the within-subject errors. If the model estimation does not converge, a reduced compound symmetry covariance structure will be used instead. Conditional on the observed data and covariates, missing ppFEV1 data due to treatment or study discontinuation will be assumed to be missing at random; consequently, no imputation of missing data will be performed.

The adjusted means and 95% confidence intervals (CI) of the average treatment effect through Day 29 (Day 15 and Day 29 only) for each triple combination, with a 2-sided *p*-value will be estimated within MMRM using PROC MIXED in SAS, for all within-treatment and between-treatment comparisons, for each part, separately. Contrasts based on the fixed effects in the model, defined at the baseline covariate mean for the combined treatment groups using unique subjects in the FAS who have at least one post-baseline measurement through Day 29, will be used to estimate the average treatment effect across post-baseline visits through Day 29.

[figure not shown]

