**8.3.5.3 Absolute Change in Sweat Chloride from Baseline through Day 29 (Parts 1 and 2)** 

**8.3.5.3.1 Parts 1 and 2**

The analysis of the absolute change in sweat chloride from baseline through Day 29 will be based on an MMRM model similar to the analysis of the primary efficacy variable in Part 1, with the continuous baseline sweat chloride as a covariate. The presentation of results will also be similar.

The adjusted mean (with 95% CI) obtained from the MMRM analysis at each post-baseline visit through Day 29 in the Treatment Period will be plotted by treatment group, for each part.

A waterfall plot showing the subject-level absolute change in sweat chloride at Day 29 will be presented, by treatment group. The plots will be based on the pooled treatment groups for Part 1.

In addition, for each part, descriptive analyses of the change from baseline will be performed for all treatment groups by post-baseline visit. Treatment groups TC-1A and TC-1B-low in Part 1 will be presented both pooled and separately, for descriptive analysis.

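### The SAP's test of zero within-group change in ppFEV1 treats the observed mean baseline as known, so within-group confidence intervals are somewhat too narrow if change depends on baseline

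*Protocol*

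**What the plan says.** SAP 8.3.1.1.1 (Parts 1 and 2) sets the primary efficacy null within group: "The null hypothesis to be tested is that the mean absolute within-group change from baseline in percent predicted FEV"1 through Day 29 is zero, for each part separately, rejected at a 2-sided p of 0.05 or less. The test comes from an MMRM of change with continuous baseline ppFEV1 as a covariate. The estimate averages Day 15 and Day 29: "Contrasts based on the fixed effects in the model, defined at the baseline covariate mean for the combined treatment groups". No term for the sampling error of that mean is described. SAP 8.3.5.3.1 uses a similar model for sweat chloride, "with the continuous baseline sweat chloride as a covariate".

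The protocol is less uniform.

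- The synopsis says that all ppFEV1 tests "will be performed within the mixed-effects model for repeated measures (MMRM) framework at a 5% alpha level". The next sentence says that the within-group null "in all treatment groups, by part, will be tested using a 2-sided 1-sample" t test, and the sentence after that takes within-group means and intervals from the MMRM.
- The synopsis uses the same wording for sweat chloride: "in all treatment groups, by Part, will be tested using a 2-sided 1-sample" t-test.
- Protocol 12.3.3.1 names no 1-sample test. Within-group means, intervals and P values "will be estimated within MMRM using LSMeans via PROC MIXED in SAS, for all within-group and between-group comparisons in all parts". Its visible covariates are "stratification factors at randomization as categorical covariates, when applicable"; the SAP uses continuous baseline ppFEV1.
- The power tables for ppFEV1 (Protocol 12.1.1.2, SAP 6.2.1.2) are for a 2-sided 1-sample t test.

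**The concern.** An adjusted group mean at the sample baseline mean estimates the population mean change only if that sample mean is close to the population one. The fixed-effects standard error does not carry the uncertainty in that step. The Day 1 value is also subtracted inside the outcome, so noise in it makes high baselines fall and low ones rise. That alone gives change a non-zero slope on baseline.

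The missing piece is common to all groups, so it cancels in a difference between groups. It does not cancel in a single group's mean, and that is the quantity in the stated primary null. At stake are the level of the 0.05 rule and the coverage of the within-group 95% intervals. The error runs towards declaring a change. The plan makes no multiplicity adjustment that might absorb it.

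**Working it through.** **Plan's own figure.** Exact non-central t power for a 2-sided 1-sample t test with SD 8 and n = 16 gives 29.0, 46.5, 64.7, 80.1 and 90.5% for changes of 3, 4, 5, 6 and 7 points. Protocol Table 12-2 gives 29, 46, 65, 80 and 90%. All 40 cells agree within 2 points, so the planned power belongs to the unadjusted test.

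**Group sizes from the documents.** Cohort 1A: 10 at 4:1 gives 8 and 2. Cohort 1B: 32 at 2:1:1 gives 16, 8 and 8. The Part 1 model therefore has high 16, pooled low 8 + 8 = 16 and placebo 2 + 8 = 10, N = 42. Part 2: 24 at 3:1 gives TC-2 18 and TEZ/IVA 6.

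**Variance.** Let b be the slope of change on baseline, R² the share of the variance of change that baseline explains, n the group size and N the model total. Ignoring a small imbalance term:

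- reported variance = (1 − R²)·SD²/n
- variance for the stated null = (1 − R²)·SD²/n + R²·SD²/N, where R²·SD² = b²·Var(baseline)

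Reported SE as a share of the true SE, and the resulting type I error (t with N − groups − 1 df):

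| R² | Part 1 TC group (16 of 42) | Part 2 TC-2 (18 of 24) |
|---|---|---|
| 0 | 1.000, 5.0% | 1.000, 5.0% |
| 0.1 | 0.979, 5.5% | 0.961, 5.9% |
| 0.2 | 0.956, about 6.1% | 0.918, 7.0% |
| 0.3 | 0.927, 6.8% | 0.870, 8.5% |

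**What R² might be (assumption).** The documents give no slope, R² or baseline SD. Eligibility at 40 to 90% predicted makes a between-subject SD of 10 to 18 plausible; a uniform spread over that range has SD 50/√12 = 14.4. Assume that 60 to 100% of the variance of change is visit-to-visit noise. The outcome is the mean of two readings minus one, so the noise variance per reading is share × 64/1.5.

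Worked case, Part 2, between-subject SD 14, all noise:

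- noise variance 64/1.5 = 42.7; Var(baseline) = 196 + 42.7 = 238.7; b = −42.7/238.7 = −0.179
- b²·Var(baseline) = 42.7²/238.7 = 7.6; residual variance 64 − 7.6 = 56.4; R² = 7.6/64 = 0.12
- reported SE = √(56.4/18) = 1.77; true SE = √(56.4/18 + 7.6/24) = 1.86
- type I error about 6.1%; at 60% noise, 5.4%

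Over the whole assumed range R² runs from 0.03 (SD 18, 60% noise) to 0.20 (SD 10, all noise). The formula gives 5.2 to 7.0% for TC-2 and 5.1 to 6.1% for a Part 1 triple-combination group. Simulated null trials (20,000 to 40,000 per setting, normal data, complete follow-up) span about 5.1 to 7.1% and 5.0 to 6.1%. An unstructured two-visit REML fit agrees within Monte Carlo error.

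**Sweat chloride.** With SD 13 from the plan, an assumed between-subject SD of 10 to 15 and the same noise shares, R² runs from about 0.09 to 0.35. Simulated type I error is about 5.7 to 9.3% in Part 2 and 5.2 to 7.4% in Part 1.

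**Controls.** On the ppFEV1 settings, a 1-sample t test gave 4.8 to 5.3%. Adding b̂²·s²/N to the squared SE gave 4.4 to 5.1%. Between-group tests stayed at 4.8 to 5.2%. The dose-response contrasts in SAP Table 6-5 each sum to zero (1 + 0 − 1; 1 − 0.5 − 0.5; 0.5 + 0.5 − 1), so the common term cancels.

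**Effect on a decision.** In the worked case the critical t on 21 df is 2.080. The verdict changes only for an observed TC-2 mean between 2.080 × 1.77 = 3.68 and 2.080 × 1.86 = 3.87 points. A mean of 3.8 gives p = 0.044 with the reported SE and 0.054 with the true SE. A mean of 5 gives 0.010 and 0.014; a mean of 7 gives about 0.001 with either.

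**The case against.** The strongest reply is that inference at the observed covariate mean is a common convention. Conditional on that mean, the test holds its level: 4.8 to 5.2% in simulation. That is true, but SAP 8.3.1.1.1 states its null without that condition, and the power tables are for an unconditional test.

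The excess also rests on a slope that neither document gives. That stands. A reader might infer that the test always rejects above 5%; at slope zero it does not.

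A reader might also infer that the SAP replaced a pre-specified test. The documents do not support that. The synopsis places ppFEV1 tests in the MMRM, and Protocol 12.3.3.1 takes within-group P values from it. What remains is loose synopsis wording and a power basis that differs from the analysis.

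It might further seem that baseline adjustment buys no real precision for a within-group mean. The real share of the reported variance reduction is 1 − n/N: 1 − 18/24 = 25% for TC-2, but 1 − 16/42 = 62% in Part 1. Dropping the covariate, or reverting to the 1-sample test, would discard that gain. The t test would also need a rule for a missing visit, which the MMRM handles under missing at random.

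Finally, unadjusted changes by visit are reported descriptively, and parts of the SAP's efficacy section are redacted, so the absence of a supportive analysis cannot be inferred.

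**Conclusion.** The point holds in a limited form. For the null that the SAP states, the within-group standard error is too small whenever change depends on baseline. Part 2 is more exposed because TC-2 is 75% of its model total. For ppFEV1 the excess is small: about 5.1 to 7.1% for TC-2 and 5.0 to 6.1% for the Part 1 triple-combination groups, under the assumed baseline SD and noise share. Sweat chloride could reach about 9% in Part 2, because under the assumptions baseline there explains more of the change. Decisions would rarely alter at the 5 to 7 point changes that the plan expects. Between-group results and the dose-response test are sound on this point. The correction is worth making because it concerns the stated primary decision rule and is cheap.

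**What to change.** Keep the baseline-adjusted MMRM for all between-group contrasts. For within-group means, intervals and p-values in SAP 8.3.1.1.1, 8.3.2.1, 8.3.2.2 and 8.3.5.3, use one of the following:

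- Add the variance of the baseline mean, b̂²·s²/N, to the squared SE, with b̂ the slope for the averaged visits and s² the sample variance of baseline. CFQ-R has two continuous baseline covariates, so the term uses their slopes and sample covariance matrix.
- For the absolute-change endpoints, fit the MMRM with Day 1, Day 15 and Day 29 as responses and unstructured covariance, and contrast the post-baseline average (Day 29 alone for CFQ-R) with Day 1. Specify a Day 1 mean common to the groups of a part. This keeps the real precision gain and the missing-at-random handling; with separate Day 1 means and complete data, the estimate falls back to the unadjusted change.

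Reword the two synopsis sentences on the 1-sample t test, for ppFEV1 and sweat chloride, so that they name this same MMRM-based test.

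The cost is SAP wording, one more model call and within-group ppFEV1 intervals about 1 to 10% wider. Data collection, visits and sample size do not change.

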3 SCHEDULE OF ASSESSMENTS

The schedule of assessments from the Screening Period through the Safety Follow-up Visit are provided in [Table 3-1](#) for Part 1 Cohort 1A, [Table 3-2](#) for Part 1 Cohort 1B, [Table 3-3](#) for Part 2, [REDACTED]

All visits will be scheduled relative to the Day 1 Visit (first dose of VX-440 or VX-440 matched placebo).

The CFQ-R assessment must be completed before any other assessment at the clinic visits when it is required. For remaining assessments, assessments may be performed in any order when more than 1 assessment is required at a particular time point. (See [Section 11.1.](#))

Table 3-1 Study VX15-440-101: Schedule of Assessments for Part 1 (Cohort 1A)

Event/Assessment ^a	Screening	Treatment Period ^b				Day 43 (± 3 days)	ETT Visit ^c	Safety Follow-up 28 (± 7) Days After Last Dose
	Days -28 to -1 ^d	Day 1	Day 8 (± 1 day)	Day 15 (± 2 days)	Day 29 (± 2 days)			
Informed consent	X							
Randomization ^e		X						
Demographics	X							
Medical history	X							
Ophthalmological history	X							
CFQ-R ^{f,g}		X		X	X	X	X ^h	X
Weight ⁱ	X	X	X	X	X	X	X	X
Height ⁱ	X							
Vital signs ^j	X	X	X	X	X	X	X	X
Pulse oximetry ^j	X	X	X	X	X	X	X	X

^a All assessments will be performed before dosing, unless noted otherwise. Assessments that are collected before and after dosing will only be collected once if study drug is not administered on the day of the visit (i.e., if subject prematurely discontinued study drug treatment).

^b To be eligible to continue into the Treatment Period, subjects must have stable CF disease and have remained on stable CF medication regimen during the 28 days before the Day 1 Visit AND must not have had an acute non-CF illness within 14 days before the Day 1 Visit. See [Section 8.1.3](#).

^c If the subject prematurely discontinues study treatment, an ETT Visit should be scheduled as soon as possible after the decision to terminate study drug treatment. Subjects who prematurely discontinue treatment will also be required to complete the Safety Follow-up Visit. If the ETT Visit occurs 3 weeks or later following the last dose of study drug, then the ETT Visit will replace the Safety Follow-up Visit, and a separate Safety Follow-up Visit will not be required.

^d All screening results must be reviewed by an appropriately qualified member of the investigator's team before randomization, unless noted otherwise.

^e Randomization may occur on the previous day (Day -1) after all inclusion and exclusion criteria have been confirmed.

^f CFQ-R must be completed before the start of any other assessments scheduled at that visit.

^g The predose assessment on Day 1 may be performed on the previous day (Day -1) if randomization has occurred.

^h Subjects will complete the CFQ-R at the ETT Visit only if it has been 2 weeks or more since their last visit.

ⁱ Weight and height will be measured with shoes off.

^j Vital signs and pulse oximetry will be collected after the subject has been seated for at least 5 minutes.

Table 3-1 Study VX15-440-101: Schedule of Assessments for Part 1 (Cohort 1A)

Event/Assessment ^a	Screening	Treatment Period ^b				Day 43 (± 3 days)	ETT Visit ^c	Safety Follow-up 28 (± 7) Days After Last Dose
	Days -28 to -1 ^d	Day 1	Day 8 (± 1 day)	Day 15 (± 2 days)	Day 29 (± 2 days)			
Physical examination ^k	Complete	Abbreviated		Abbreviated	Abbreviated		Abbreviated	Complete
Ophthalmologic examination ^l	X							
Standard 12-lead ECG ^m	X	X	X	X	X	X	X	X
Sweat chloride ^{g,n}	X	X	X	X	X	X	X	X
Spirometry ^o	X	X	X	X	X	X	X	X
Urinalysis ^g	X	X	X	X	X	X	X	X
Pregnancy test (all females of childbearing potential)	Serum	Urine			Urine		Serum	Serum
CFTR genotype ^p	X							
FSH ^q	X							

^k Complete and abbreviated PEs are described in [Section 11.7.3](#). Symptom-targeted PEs will occur at any time during the study if triggered by AEs or if deemed necessary by the investigator or healthcare provider.

^l The ophthalmological examination can be performed at any time during the Screening Period through the Day 1 Visit (before the first dose of study drug). The screening ophthalmological examination does not have to be performed if there is documentation of an examination that met protocol criteria and was within 3 months before the date of informed consent, or if there is documentation of bilateral lens removal for the subject.

^m All standard 12-lead ECGs will be performed after the subject has been seated for at least 5 minutes. On Days 1 and 15, ECGs will be collected before dosing and 4 hours (± 1 hour) after dosing. At all other visits, ECGs will be collected before dosing (as applicable). ECGs collected on Day 1 before dosing will be performed in triplicate.

ⁿ Sweat chloride will be measured in all subjects. If the value cannot be determined from the screening test, a sweat chloride value documented in the subject's medical record may be used to establish eligibility.

^o Spirometry may be performed pre- or post-bronchodilator at the Screening Visit. Spirometry will be performed pre-bronchodilator, before the morning dose of study drugs, and should be performed at approximately the same time at every other study visit. On Days 1 and 15, spirometry will also be performed pre-bronchodilator 5 hours (± 1 hour) after study drug administration.

^p *CFTR* genotyping will be performed for all subjects. If the screening *CFTR* genotype result is not received before randomization, a previous *CFTR* genotype laboratory report may be used to establish eligibility.

^q FSH will be measured for any suspected postmenopausal female subjects with at least 12 months of continuous spontaneous amenorrhea.

Table 3-1 Study VX15-440-101: Schedule of Assessments for Part 1 (Cohort 1A)

Event/Assessment ^a	Screening	Treatment Period ^b				Day 43 (± 3 days)	ETT Visit ^c	Safety Follow-up 28 (± 7) Days After Last Dose
	Days -28 to -1 ^d	Day 1	Day 8 (± 1 day)	Day 15 (± 2 days)	Day 29 (± 2 days)			
G6PD activity test ^f	X							
Serum chemistry and hematology ^g	X	X	X	X	X	X	X	X
Coagulation ^g	X	X		X	X			X
PK sampling ^h		X	X	X	X	X	X	
Study drug dosing ^u		Day 1 through Day 29						
AEs, medications ^v , treatments, and procedures	Continuous from signing of the ICF through the Safety Follow-up Visit							

r

Blood samples will be collected for PK analysis of VX-440, TEZ, M1-TEZ, IVA, and M1-IVA. On Day 1, samples will be collected before dosing (0 hours) and at 1, 2, 4, and 6 hours after dosing (relative to the morning dose). On Days 8 and 29, a predose sample will be collected before the morning dose of study drug. On Day 15, samples will be collected before dosing (0 hours) and at 1, 2, 4, 6, and 8 hours after dosing. At the Day 43 and the ETT Visits, a single blood sample for PK analysis will be collected.

^u The last dose of study drug will be the morning dose on Day 29.

^v Refer to [Section 9.4](#) for details.

Table 3-2 Study VX15-440-101: Schedule of Assessments for Part 1 (Cohort 1B)

Event/Assessment ^a	Screening	Treatment Period ^b			Day 43 (± 3 days)	ETT Visit ^c	Safety Follow-up 28 (± 7) Days After Last Dose
	Days -28 to -1 ^d	Day 1	Day 15 (± 2 day)	Day 29 (± 2 day)			
Informed consent	X						
Randomization ^e		X					
Demographics	X						
Medical history	X						
Ophthalmological history	X						
CFQ-R ^{f,g}		X	X	X	X	X ^h	X
Weight ⁱ	X	X	X	X	X	X	X
Height ⁱ	X						
Vital signs ^j	X	X	X	X	X	X	X
Pulse oximetry ^j	X	X	X	X	X	X	X

- ^a All assessments will be performed before dosing, unless noted otherwise. Assessments that are collected before and after dosing will only be collected once if study drug is not administered on the day of the visit (i.e., if subject prematurely discontinued study drug treatment).
- ^b To be eligible to continue into the Treatment Period, subjects must have stable CF disease and have remained on stable CF medication regimen during the 28 days before the Day 1 Visit AND must not have had an acute non-CF illness within 14 days before the Day 1 Visit. See [Section 8.1.3](#).
- ^c If the subject prematurely discontinues study drug treatment, an ETT Visit should be scheduled as soon as possible after the decision to terminate study drug treatment. Subjects who prematurely discontinue treatment will also be required to complete the Safety Follow-up Visit. If the ETT Visit occurs 3 weeks or later following the last dose of study drug, then the ETT Visit will replace the Safety Follow-up Visit, and a separate Safety Follow-up Visit will not be required.
- ^d All screening results must be reviewed by an appropriately qualified member of the investigator's team before randomization, unless noted otherwise.
- ^e Randomization may occur on the previous day (Day -1) after all inclusion and exclusion criteria have been confirmed.
- ^f CFQ-R must be completed before the start of any other assessments scheduled at that visit.
- ^g The predose assessment on Day 1 may be performed on the previous day (Day -1) if randomization has occurred.
- ^h Subjects will complete the CFQ-R at the ETT Visit only if it has been 2 weeks or more since their last visit.
- ⁱ Weight and height will be measured with shoes off.
- ^j Vital signs and pulse oximetry will be collected after the subject has been seated for at least 5 minutes.

Table 3-2 Study VX15-440-101: Schedule of Assessments for Part 1 (Cohort 1B)

Event/Assessment ^a	Screening	Treatment Period ^b			Day 43 (± 3 days)	ETT Visit ^c	Safety Follow-up 28 (± 7) Days After Last Dose
	Days -28 to -1 ^d	Day 1	Day 15 (± 2 day)	Day 29 (± 2 day)			
Physical examination ^k	Complete	Abbreviated	Abbreviated	Abbreviated		Abbreviated	Complete
Ophthalmologic examination ^l	X						
Standard 12-lead ECG ^m	X	X	X	X	X	X	X
Sweat chloride ^{g,n}	X	X	X	X	X	X	X
Spirometry ^o	X	X	X	X	X	X	X
Urinalysis ^g	X	X	X	X	X	X	X
Pregnancy test (all females of childbearing potential)	Serum	Urine		Urine		Serum	Serum
CFTR genotype ^p	X						
FSH ^q	X						

^k Complete and abbreviated PEs are described in [Section 11.7.3](#). Symptom-targeted PEs will occur at any time during the study if triggered by AEs or if deemed necessary by the investigator or healthcare provider.

^l The ophthalmological examination can be performed at any time during the Screening Period through the Day 1 Visit (before the first dose of study drug). The screening ophthalmological examination does not have to be performed if there is documentation of an examination that met protocol criteria and was within 3 months before the date of informed consent, or if there is documentation of bilateral lens removal for the subject.

^m All standard 12-lead ECGs will be performed after the subject has been seated for at least 5 minutes. On Days 1 and 15, ECGs will be collected before dosing and 4 hours (± 1 hour) after dosing. At all other visits, ECGs will be collected before dosing (as applicable). ECGs collected on Day 1 before dosing will be performed in triplicate.

ⁿ Sweat chloride will be measured in all subjects. If the value cannot be determined from the screening test, a sweat chloride value documented in the subject's medical record may be used to establish eligibility.

^o Spirometry may be performed pre- or post-bronchodilator at the Screening Visit. Spirometry will be performed pre-bronchodilator, before the morning dose of study drugs, and should be performed at approximately the same time at every other study visit. On Days 1 and 15, spirometry will also be performed pre-bronchodilator, 5 hours (± 1 hour) after study drug administration.

^p *CFTR* genotyping will be performed for all subjects. If the screening *CFTR* genotype result is not received before randomization, a previous *CFTR* genotype laboratory report may be used to establish eligibility.

^q FSH will be measured for any suspected postmenopausal female subjects with at least 12 months of continuous spontaneous amenorrhea.

Table 3-2 Study VX15-440-101: Schedule of Assessments for Part 1 (Cohort 1B)

Event/Assessment ^a	Screening	Treatment Period ^b			Day 43 (± 3 days)	ETT Visit ^c	Safety Follow-up 28 (± 7) Days After Last Dose
	Days -28 to -1 ^d	Day 1	Day 15 (± 2 day)	Day 29 (± 2 day)			
G6PD activity test ^f	X						
Serum chemistry and hematology ^g	X	X	X	X	X	X	X
Coagulation ^g	X	X	X	X			X
PK sampling ^h		X	X	X	X	X	
Study drug dosing ^u		Day 1 through Day 29					
AEs, medications ^v , treatments and procedures	Continuous from signing of the ICF through the Safety Follow-up Visit						

^f A single blood sample will be collected for the G6PD activity test.

Blood samples will be collected for PK analysis of VX-440, TEZ, M1-TEZ, IVA, and M1-IVA. On Day 1, samples will be collected before dosing (0 hours) and at 1, 2, 4, and 6 hours after dosing (relative to the morning dose). On Day 15, samples will be collected before dosing (0 hours) and at 1, 2, 4, 6, and 8 hours after dosing. On Day 29, a predose sample will be collected before the morning dose of study drug. At the Day 43 and the ETT Visits, a single blood sample for PK analysis will be collected.

^u The last dose of study drug will be the morning dose on Day 29.

^v Refer to [Section 9.4](#) for details.

Table 3-3 Study VX15-440-101: Schedule of Assessments for Part 2

Event/Assessment ^a	Screening	Run-in Period		Treatment Period ^b			Washout Period		ETT Visit ^c	Safety Follow-up 28 (± 7) Days After Last Dose ^d
	Days -56 to -29 ^e	Day -28 (± 1 day)	Day -14 ^f (± 1 day)	Day 1	Day 15 (± 2 days)	Day 29 (± 2 days)	Day 43 (± 3 days)	Day 57 (± 3 days)		
Informed consent	X									
Randomization ^g				X						
Demographics	X									
Medical history	X									
Ophthalmological history	X									
CFQ-R ^{h,i}				X	X	X	X	X	X ^j	X
Weight ^k	X	X		X	X	X	X	X	X	X
Height ^k	X									
Vital signs ^l	X	X		X	X	X	X	X	X	X
Pulse oximetry ^l	X	X		X	X	X	X	X	X	X

^a All assessments will be performed before dosing, unless noted otherwise. Assessments that are collected before and after dosing will only be collected once if study drug is not administered on the day of the visit (i.e., if subject prematurely discontinued study drug treatment).

^b To be eligible to continue into the Treatment Period, subjects must have stable CF disease and have remained on stable CF medication regimen during the 28 days before the Day 1 Visit AND must not have had an acute non-CF illness within 14 days before the Day 1 Visit. See [Section 8.1.3](#).

^c If the subject prematurely discontinues study treatment, an ETT Visit should be scheduled as soon as possible after the decision to terminate study drug treatment. Subjects who prematurely discontinue treatment will also be required to complete the Safety Follow-up Visit. If the ETT Visit occurs 3 weeks or later following the last dose of study drug, then the ETT Visit will replace the Safety Follow-up Visit, and a separate Safety Follow-up Visit will not be required.

^d Part 2 subjects who meet criteria specified in [Section 8.1.5](#) will not have a Safety Follow-up Visit.

^e All screening results must be reviewed by an appropriately qualified member of the investigator's team before the subject receives the first dose of TEZ/IVA in the Run-in Period on Day -28, unless noted otherwise.

^f The Day -14 Visit is only required for subjects who are naïve to TEZ/IVA treatment.

^g Randomization may occur on the previous day (Day -1) after all inclusion and exclusion criteria and criteria for entry into the Treatment Period have been confirmed. See [Section 8.1.3](#).

^h CFQ-R must be completed before the start of any other assessments scheduled at that visit.

ⁱ The predose assessment on Day 1 may be performed on the previous day (Day -1) if randomization has occurred.

^j Subjects will complete the CFQ-R at the ETT Visit only if it has been 2 weeks or more since their last visit.

^k Weight and height will be measured with shoes off.

^l Vital signs and pulse oximetry will be collected after the subject has been seated for at least 5 minutes.

Table 3-3 Study VX15-440-101: Schedule of Assessments for Part 2

Event/Assessment ^a	Screening	Run-in Period		Treatment Period ^b			Washout Period		ETT Visit ^c	Safety Follow-up 28 (± 7) Days After Last Dose ^d
	Days -56 to -29 ^e	Day -28 (± 1 day)	Day -14 ^f (± 1 day)	Day 1	Day 15 (± 2 days)	Day 29 (± 2 days)	Day 43 (± 3 days)	Day 57 (± 3 days)		
Physical examination ^m	Complete	Abbreviated		Abbreviated	Abbreviated	Abbreviated		Abbreviated	Abbreviated	Complete
Ophthalmologic examination ⁿ	X									
Standard 12-lead ECG ^o	X	X		X	X	X	X	X	X	X
Sweat chloride ^{i,p}	X		X	X	X	X	X	X	X	
Spirometry ^q	X		X	X	X	X	X	X	X	X
Urinalysis ^r	X	X		X	X	X	X	X	X	X
Pregnancy test (all females of childbearing potential)	Serum	Urine		Urine		Urine		Urine	Serum	Serum
CFTR genotype ^r	X									
FSH ^s	X									

